5.3 Image interpretation

The PET/MRI scans will be interpreted by ABNM certified Nuclear Medicine physicians and an ABR certified Radiologists. Drs [name], [name], [name], and [name] have significant clinical experience and will be blinded to the participants' medical history and the results of other imaging modalities. Consensus read will be obtained for each scan. Each lesion will be tabulated and a comparison of lesion detection by each tracer will be conducted.

The study team will communicate the results of the scans to the referring (treating) physicians. Additional imaging/biopsy may be performed as a result of the research scan data.

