5. Approximately 45 to 60 minutes after the radiopharmaceutical IV administration, data acquisition will begin in the pelvic region and move toward the head. First, localizer MRI scans will be performed to define the table positions. After correct positioning of the spatial acquisition windows is ensured, the combined PET/MRI acquisition will be initiated with 3 to 5 table positions at a 2 to 4 minute acquisition time per table position. Only MR sequences required for attenuation correction of PET data will be acquired.
6. Vital signs (heart rate, blood pressure) will be recorded again at the completion of the study.
7. Participants will be contacted at 24 to 72 hours following the scan in order to capture potential occurring Adverse Events.

The above will be repeated approximately 6 months after HIFU local treatment, prior to standard of care biopsy to evaluate for residual disease in the prostate.

Objectives of the Study

Primary Objective

- To determine feasibility of ^{68}Ga -PSMA-11 PET/MRI and ^{68}Ga -RM2 PET/MRI for evaluation of HIFU local therapy in patients with known prostate cancer.

Secondary Objective

- None

Exploratory Objectives

- Comparison of ^{68}Ga -PSMA-11 post-treatment uptake and pre-post change in uptake in response to HIFU local therapy
- Comparison of ^{68}Ga -RM2 post-treatment uptake and pre-post change in uptake in response to HIFU local therapy

Endpoints

Primary Endpoints

- Number of participants with assessable pre- and post-treatment uptake in response to HIFU local therapy

Secondary Endpoint

- None

Exploratory Endpoints

- Pre- and post-treatment ^{68}Ga -PSMA-11 SUV_{\max} and pre-post change in SUV_{\max} after HIFU local therapy
- Pre- and post-treatment ^{68}Ga -RM2 SUV_{\max} and pre-post change in SUV_{\max} after HIFU local therapy

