6.3 Follow-up

Active subject participation ends after the 24 to 72 hour Safety Follow-up after the 2nd post-therapy scan. Investigators will follow subjects by chart review for 12 months post-scan to record any standard of care biopsies or imaging results. The investigators will assist with identification of lesions that can be biopsied, based on ⁶⁸Ga-RM2 and/or ⁶⁸Ga-PSMA11 PET/MRI findings.

If a subject transfers clinical care outside of Stanford Healthcare during the chart review clinical follow-up period, investigators will request permission to contact the treating physician.

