10.4 Analyses Plans

This is a pilot study that will not have pre-defined analyses plans, other than the described assessment for the number of participants for which a PET--based therapeutic response to HIFU successfully obtained. We will compare the changes in SUV_{max} after HIFU local therapy with results of biopsy done as standard of care at 6 months post-treatment, as well as with PSA values done every 3 months afterwards (ie, a decrease in uptake is expected to predict response, while stable or increased uptake is expected to indicate no response to HIFU local therapy). Data from 2 arms ($^{68}\text{Ga-PSMA11}$ done first or $^{68}\text{Ga-RM2}$ done first) will be aggregated. In the case that the treatment has worked to extent that the primary tumor is no longer visible, the disappearance will be detectable because of the correspondence between pre and post ROIs. In that case, we will consider the tumor assessable, and record the SUV_{max} as the ROI background.

There is no analysis beyond noting whether the total number of assessable patients meets or exceeds the threshold for success (10 of 20).

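### The post-HIFU scan may influence the 6-month biopsy it is compared with, and the plan does not record or separate scan-directed sampling

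*Combined protocol and SAP*

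**What the plan says.** Section 2.5 places the repeat scans about six months after HIFU, "prior to standard of care biopsy to evaluate for residual disease in the prostate". Section 5.2 and footnote a of the section 7 calendar give the same order.

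Section 5.3 says: "The study team will communicate the results of the scans to the referring (treating) physicians". The next sentence is: "Additional imaging/biopsy may be performed as a result of the research scan data". It also says: "Each lesion will be tabulated and a comparison of lesion detection by each tracer will be conducted".

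Section 6.3 says: "The investigators will assist with identification of lesions that can be biopsied, based on" the findings with either or both tracers. It also says: "Investigators will follow subjects by chart review for 12 months post-scan to record any standard of care biopsies or imaging results".

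Section 10.4 undertakes to compare the change in SUVmax "after HIFU local therapy with results of biopsy done as standard of care at 6 months post-treatment", and with later PSA values. A fall in uptake is taken to predict response; stable or rising uptake is taken to mean no response. The same section opens with "This is a pilot study that will not have pre-defined analyses plans", apart from the count of assessable participants, and closes by saying that nothing is analysed beyond that count. Section 10.2 expects 1 to 2 patients with residual tumour.

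**The concern.** A reference standard should not depend on the test being judged against it. Here the scan comes first, its result is released with no hold until after the biopsy, and the investigators may point to lesions worth sampling. A man with a suspicious scan may then get targeted cores that a man with a quiet scan does not. If targeted cores find tumour more often, a residual tumour the scan sees is more likely to be confirmed than one it misses, and scan and biopsy appear to agree better than they do.

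Only the exploratory comparison in 10.4 is at stake. Because it will rest on one or two tumours, a reader needs to know whether a confirming core was taken because of the scan. If this is not noted at the time, it may be impossible to recover later.

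**Working it through.** The plan gives no figure to reproduce on this point. The check has a textual part and an illustrative part.

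**1. Text.** The post-HIFU scan precedes the biopsy (2.5, 5.2, section 7). Results go to the treating physicians, and biopsy may follow from them (5.3). The investigators help identify lesions for biopsy from the PET findings (6.3). The 6-month biopsy is the comparator (10.4). No section delays release, fixes a biopsy template, or blinds the operator or the pathologist to the scan. The blinding in 5.3 covers the image readers only. Sections 6.3, 7, 10.1 and 10.4 contain no item for whether a biopsy or core was scan-directed, and no split of the comparison. The CRFs are not in the documents, so this is a statement about the protocol text only.

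**2. Direction and possible size of the effect.** All inputs are assumed; none is in the documents. Sensitivity is not a planned endpoint. I use it only as a yardstick for agreement: the share of biopsy-confirmed residual tumours that the scan calls positive.
- s = true sensitivity, 0.5 to 0.8
- b0 = detection with usual cores only, 0.5 to 0.8
- b1 = detection with usual plus directed cores, 0.85 to 0.95
- f = share of scan-positive men who get directed cores

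Detection in scan-positive men is bp = f × b1 + (1 − f) × b0. Apparent sensitivity is s × bp / [s × bp + (1 − s) × b0].

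Largest case: f = 1, s = 0.5, b0 = 0.5, b1 = 0.95 gives 0.475 / (0.475 + 0.25) = 0.655, or +15.5 points. Smallest case with f = 1: s = 0.8, b0 = 0.8, b1 = 0.85 gives 0.68 / (0.68 + 0.16) = 0.810, or +1.0 point.

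| f | Bias in points |
|---|---|
| 1 | +1.0 to +15.5 |
| 0.5 | +0.5 to +9.2 |
| 0.25 | +0.2 to +5.1 |
| 0, or b0 = b1 | 0 |

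The formula assumes that directed cores go to men whose scan counts as no response. A lesion with reduced but still visible uptake could also be targeted, and that would pull the other way.

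**3. What one or two tumours would show.** Take one scan-positive and one scan-negative residual tumour, with b1 = 0.9. An entry x/y means x scan-positive among y confirmed; 1/2 is the true table. With direction, the probabilities are b1 × b0 for 1/2, b1 × (1 − b0) for 1/1 and (1 − b1) × b0 for 0/1. Without it, they are b0² for 1/2 and b0 × (1 − b0) for each of 1/1 and 0/1.

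| b0 | Directed 1/2 | Directed 1/1 | Directed 0/1 | Usual 1/2 | Usual 1/1 | Usual 0/1 |
|---|---|---|---|---|---|---|
| 0.50 | 0.45 | 0.45 | 0.05 | 0.25 | 0.25 | 0.25 |
| 0.65 | 0.585 | 0.315 | 0.065 | 0.4225 | 0.2275 | 0.2275 |
| 0.80 | 0.72 | 0.18 | 0.08 | 0.64 | 0.16 | 0.16 |

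Direction makes the true table more likely. It also makes errors lopsided: the table that flatters the scan (1/1) becomes more likely than without direction, and its opposite (0/1) less likely.

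**4. Sampling error.** The exact 95% lower limit is 0.025 for 1/1, and √0.025 = 0.158 for 2/2. Both uncertainties far exceed the bias in step 2.

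**5. What labelling could reveal.** If usual cores are also taken, a scan-positive tumour would be found only in directed cores with probability b1 − b0 = 0.40, 0.25 or 0.10 for b0 = 0.5, 0.65 or 0.8.

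**The case against.** The strongest objection is that the link to the reference biopsy is inferred. Section 5.3 speaks of additional biopsy, which most naturally means procedures beyond the scheduled one, and 6.3 names no particular biopsy. If scan-prompted biopsies are always separate and stay out of the 10.4 comparison, the bias is zero. A reader might infer that the scan will direct the 6-month biopsy. The text does not say so; it only leaves the overlap open. That limits the point but does not remove it, because nothing keeps the two apart.

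Second, sensitivity is nowhere an objective or endpoint, and 10.4 disclaims planned analysis. That stands against any claim of a biased result. But 10.4 also commits to the comparison, so how the biopsy was obtained still matters to whoever reads it.

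Third, every magnitude is assumed and sampling error is larger. Both are true. Sampling error can be read from the counts, however; the origin of a core cannot.

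Fourth, directed sampling finds more true residual tumour. This stands, and it is why release and targeting should not be restricted.

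Fifth, dropping directed cores does not restore an independent reference, since an operator who knows the scan may place usual cores accordingly, and a target may come from the MRI component. This also stands and shapes the fix.

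Finally, lesions are already tabulated by tracer and biopsy results collected by chart review, and the CRFs may hold more. If they already capture direction, only the reporting change remains.

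**Conclusion.** The concern holds as a minor one. The plan allows the post-HIFU scan to influence the biopsy that serves as comparator for SUVmax change, and it neither records nor separates such sampling. The exploratory agreement may therefore be overstated. The bias arises only if direction of the 6-month biopsy actually occurs and directed cores detect better than usual ones. The documents do not allow its amount to be estimated; the 0 to 15.5 points above illustrate assumed inputs and do not predict this trial's bias.

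A reader might go further and conclude that the feasibility result is compromised. It is not: the 10-of-20 rule counts assessable scans and uses no biopsy, and the PSA comparison does not depend on where cores are taken.

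**What to change.** Leave result release and scan-directed biopsy as they are.

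- **Section 6.3:** for each biopsy after a study scan, record by chart review whether the operator knew the scan result and whether the scan prompted the biopsy. Where the biopsy or pathology report allows, also record which cores were directed, and by which tracer or by MRI.
- **Section 10.4:** report the SUVmax-change comparison on all cores and again excluding scan-directed cores, with the number of cancers found only in directed cores. State that the restricted comparison is a sensitivity check and not an unbiased reference, because usual cores may also be placed with knowledge of the scan.

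The cost is a few chart-review fields, core labelling where reports permit, and a few sentences in the two sections. No scan, read, visit or core is added. The downsides are that some reports will not identify directed cores, that the restricted comparison detects less tumour, and that with 1 to 2 residual tumours the result is descriptive only.

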6. STUDY PROCEDURES

6.1 Pre-Study

Potential subjects will be referred by treating physicians for participation in this imaging study. The following procedures will occur pre-study:

- Review of eligibility criteria
- Obtain informed consent
- Collect demographics
- Review medical history, including any concomitant medication.

6.2 Imaging Days

Subjects will undergo 2 separate clinic visits not less than 3 days apart for imaging before therapy and two separate clinic visits for imaging after therapy. After the 1st scan, the 2nd scan will only occur after the follow-up with the patient for the 1st scan, and after a minimum of 3 days have elapsed. On each imaging day, subjects will receive an intravenous (IV) injection of investigational

imaging agent (⁶⁸Ga-RM2 or ⁶⁸Ga-PSMA11) and undergo PET/MRI image collection as described above.

6.3 Follow-up

Active subject participation ends after the 24 to 72 hour Safety Follow-up after the 2nd post-therapy scan. Investigators will follow subjects by chart review for 12 months post-scan to record any standard of care biopsies or imaging results. The investigators will assist with identification of lesions that can be biopsied, based on ⁶⁸Ga-RM2 and/or ⁶⁸Ga-PSMA11 PET/MRI findings.

If a subject transfers clinical care outside of Stanford Healthcare during the chart review clinical follow-up period, investigators will request permission to contact the treating physician.

6.4 Criteria for Removal from Study

The Protocol Director may withdraw subjects from the study for one or more of the following reasons: failure to follow the instructions of the Protocol Director and/or study staff; determination that continuing the participation could be harmful to the subject; the study is cancelled or other administrative reasons.

6.5 Alternatives

The alternative is to not participate in the study.

7. STUDY CALENDAR

	Pre-Study	Scan Date	24 to 72 hours Post-Scan	12 months
Informed consent	X			
Demographics	X			
Medical history	X			
⁶⁸ Ga-RM2		X ^a		
⁶⁸ Ga-PSMA11 (\geq 3 days and \leq 2 weeks)		X ^a		
Follow-up call to participant (24 to 72 hours)			X	
Chart review ^b				X

a: Subjects will undergo either ⁶⁸Ga-RM2 PET/MRI followed within 2 weeks by ⁶⁸Ga-PSMA11 PET/MRI, or ⁶⁸Ga-PSMA11 PET/MRI followed within 2 weeks by ⁶⁸Ga-RM2 PET/MRI. After the 1st scan, the 2nd scan will only occur after the follow-up with the patient for the 1st scan, and after a minimum of 3 days have elapsed. This will be repeated approximately 6 months after HIFU local treatment, prior to standard of care biopsy to evaluate for residual disease in the prostate.

b: Subjects will be followed by chart review for 12 months from initial scan date. If a subject transfers clinical care from Stanford Healthcare, investigators may request records from the treating physician.

8. ADVERSE EVENTS AND REPORTING PROCEDURES

8.1 Potential Adverse Events

The administration of the radioactive substance will feel like a slight pinprick when given by IV injection. Patients who are claustrophobic may feel some anxiety while positioned in the scanner. Also, some patients find it uncomfortable to hold one position for more than a few minutes. The subjects will not feel anything related to the radioactivity of the substance in their body. Because the radioactivity is very short-lived, the radiation exposure is low. The substance amount is so small that it does not affect the normal processes of the body.

This research study involves exposure to radiation from two (before and after treatment) ^{68}Ga -PSMA-11 PET/MRI. There is no radiation exposure from MRI. The effective dose from one typical maximum of 259 mBq (range: 3 to 7 mCi) administration of ^{68}Ga -PSMA-11 is 6.68 mSv. Therefore, the effective dose from two ^{68}Ga -PSMA-11 PET/MRI is 13.36 mSv, approximately equal to 26% of the limit that radiation workers (eg, a hospital X-ray technician) are allowed to receive in one year.

This research study also involves exposure to radiation from two (before and after treatment) ^{68}Ga -RM2 PET/MRI. There is no radiation exposure from MRI. The amount of radiation from one administration of 140 mBq of ^{68}Ga -RM2 is 4.76 mSv. Therefore, the effective dose from two ^{68}Ga -RM2 PET/MRI is 9.52 mSv, approximately equal to 20% of the limit that radiation workers (for example, a hospital X-ray technician) are allowed to receive in one year.

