4. IMAGING AGENT INFORMATION

4.1 Study Agents ^{68}Ga -PSMA-11 and ^{68}Ga -RM2

^{68}Ga -PSMA-11

This study will use ^{68}Ga -PSMA-11 as the PET radiopharmaceutical. This agent has previously been identified as DFKZ-11; HBED-CC PSMA; or the “Heidelberg compound.”

The administered dosage of ^{68}Ga -PSMA-11 is 111 to 259 mBq (3 to 7 mCi) IV. We will use ^{68}Ga -PSMA-11 as the PET radiopharmaceutical. There are 2 publications on dosimetry for ^{68}Ga -PSMA-11 (PMID: 27260521; 28012435). The first lists 0.0236 mSv/MBq for the mean effective dose, while the other indicates 0.0258 mSv/MBq. We used the maximum potential administered activity of 7 mCi and the higher of the reported dosimetry values. Therefore, $259 \text{ mBq} \times 0.0258 \text{ mSv/MBq} = 6.68 \text{ mSv}$.

To summarize the results of the published human studies, there were no observed adverse events to the radiopharmaceutical. The measured dosimetry showed that the critical organ with ^{68}Ga -PSMA-11 is the spleen, followed by the stomach wall; pancreas; and bladder wall. The effective dose of ^{68}Ga -PSMA-11 reported (0.0258 mSv/MBq) is similar to those of ^{68}Ga -DOTA-TOC (0.023 mSv/MBq), ^{68}Ga -DOTA-NOC (0.025 mSv/MBq), ^{68}Ga -DOTA-TATE (0.021 mSv/MBq) and ^{68}Ga -NOTA-RGD (0.022 mSv/MBq) (74-77).

^{68}Ga -RM2

This study will also use ^{68}Ga -RM2 as the PET radiopharmaceutical. The administered dosage is $140 \pm 20\%$ mBq IV. Measured human dosimetry data are available from published data (78).

^{68}Ga -RM2 is rapidly excreted through the kidneys to the urinary bladder and accumulated predominantly in the pancreas and liver. Maximum peak uptake of the total injected radioactivity was seen in the urinary bladder contents and the liver, with approximately 36% and 14%, respectively.

The organ with the highest absorbed dose was the urinary bladder wall at 0.61 mSv/MBq, followed by the pancreas at 0.51 mSv/MBq. The mean effective dose (14) was 0.051 mSv/MBq. Thus, the effective dose from a 140 MBq injected radioactivity is 7.7 mSv, which could be reduced to roughly 4.76 mSv with frequent bladder voiding (1-h voids).

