To summarize the results of the published human dosimetry study, there were no observed adverse events to the radiopharmaceutical. The measured dosimetry showed that the critical organ with ^{68}Ga -RM2 is the urinary bladder, followed by the pancreas. The effective dose of ^{68}Ga -RM2 reported (0.051 mSv/MBq) is approximately twice as much as those of ^{68}Ga -DOTA-TOC (0.023 mSv/MBq), ^{68}Ga -DOTA-NOC (0.025 mSv/MBq), ^{68}Ga -DOTA-TATE (0.021 mSv/MBq) and ^{68}Ga -NOTA-RGD (0.022 mSv/MBq) (74-77).

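### Section 8.1 states the two-scan RM2 dose as 9.52 mSv without condition, but 4.1 supports that figure only with 1-h voiding; the reported mean coefficient gives 14.28 mSv

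*Combined protocol and SAP*

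**What the plan says.** Section 8.1 is where the protocol describes radiation risk. For RM2 it states "The amount of radiation from one administration of 140 mBq of ^{68}Ga -RM2 is 4.76 mSv", and for the two scans together "PET/MRI is 9.52 mSv, approximately equal to 20% of the limit that radiation workers" may receive in a year. Neither sentence mentions voiding.

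Section 4.1 is the source of these numbers. It reports "The mean effective dose (14) was 0.051 mSv/MBq". It then says the dose from 140 MBq of "injected radioactivity is 7.7 mSv, which could be reduced to roughly 4.76 mSv with frequent bladder voiding (1-h voids"). Its closing summary again uses the unreduced coefficient when comparing RM2 with other gallium-68 agents: "RM2 reported (0.051 mSv/MBq) is approximately twice as much as those of" four named tracers. On activity, 4.1 says "The administered dosage is $140 \pm 20\%$ mBq IV". (The protocol prints mBq where MBq is plainly meant.)

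On voiding, the scan steps in 2.5 ask for one or two glasses of water before arrival and a single void just before scanning, which begins about 45 to 60 minutes after injection. Neither 2.5 nor 5.2 lists a later void.

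PSMA-11 is handled differently. Section 8.1 introduces its figure as "The effective dose from one typical maximum of 259 mBq (range: 3 to 7 mCi) administration of" that agent. Section 4.1 explains that the calculation takes the top of the activity range and the larger of two published coefficients, which gives 6.68 mSv per scan and 13.36 mSv for two.

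**The concern.** A conditional, favourable value in 4.1 becomes the only value in 8.1. Someone who reads the risk section alone sees one RM2 dose and cannot tell that it depends on hourly voiding, or that the reported mean coefficient gives a figure half as large again.

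The condition matters for this agent. Section 4.1 notes "Maximum peak uptake of the total injected radioactivity was seen in the urinary bladder contents and the liver, with approximately 36% and 14%, respectively", and names the bladder wall as the organ with the highest absorbed dose. Voiding is therefore a main determinant of exposure.

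The two agents also sit side by side in 8.1 on different conventions: PSMA-11 at maximum activity and the higher coefficient, RM2 at nominal activity and the reduced dose. On the printed figures RM2 looks clearly the lower-dose agent (9.52 against 13.36 mSv). That ordering depends on the voiding assumption.

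What is at stake is the accuracy of a stated safety figure for an unapproved agent given twice to each participant. The feasibility endpoint and its threshold of 10 of 20 are untouched.

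**Working it through.** **Inputs.** From 4.1: coefficient 0.051 mSv/MBq; 7.7 mSv printed for 140 MBq; 4.76 mSv with 1-h voids; activity 140 MBq plus or minus 20%, so 112 to 168 MBq. From 8.1: two RM2 scans; 13.36 mSv for two PSMA-11 scans, called 26% of the worker limit; 9.52 mSv for two RM2 scans, called about 20%.

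**Formula.** Dose = activity x coefficient x number of scans.

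**Step 1: reproduce the plan's figure.** 2 x 4.76 = 9.52 mSv, as printed. The implied coefficient is 4.76 / 140 = 0.034 mSv/MBq, two-thirds of 0.051. The doubling in 8.1 is correct; the input is the reduced value.

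**Step 2: use the reported mean coefficient.** 140 x 0.051 = 7.14 mSv per scan, and 2 x 7.14 = 14.28 mSv. The ratio to the stated figure is 14.28 / 9.52 = 1.5.

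**Step 3: check 4.1 against itself.** 140 x 0.051 = 7.14, not 7.7. The printed 7.7 implies 7.7 / 140 = 0.055 mSv/MBq. If 7.7 is right and 0.051 is wrong, two scans give 15.40 mSv. This slip errs high and is not carried into 8.1.

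**Step 4: compare with the visible procedure.** PET acquisition is 3 to 5 table positions of 2 to 4 minutes, starting 45 to 60 minutes after injection. It ends between 45 + 3 x 2 = 51 and 60 + 5 x 4 = 80 minutes, not counting localizer or additional MR time. The one listed void falls before this and probably earns part of the reduction. As an illustration only, half the reduction means 0.0425 mSv/MBq and 2 x 140 x 0.0425 = 11.90 mSv.

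**Step 5: express against the worker limit.** The documents do not state the limit. Their percentages imply 9.52 / 0.20 = 47.6 mSv and 13.36 / 0.26 = 51.4 mSv, so I assume 50 mSv.

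| Two RM2 scans at 140 MBq | mSv | Share of 50 mSv |
|---|---|---|
| 1-h voiding (0.034) | 9.52 | 19% |
| Half the reduction (illustration) | 11.90 | 24% |
| Reported mean coefficient (0.051) | 14.28 | 29% |
| If 7.7 mSv per scan is right (0.055) | 15.40 | 31% |

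**Step 6: ordering against PSMA-11.** RM2 at 140 MBq matches 13.36 mSv when the coefficient is 13.36 / 280 = 0.0477 mSv/MBq. That corresponds to (0.051 - 0.0477) / (0.051 - 0.034), about 19% of the voiding reduction. RM2 exceeds the quoted PSMA-11 figure only if less than that is earned.

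**Step 7 (secondary): maximum permitted activity.** At 168 MBq, 2 x 168 x 0.034 = 11.42 mSv and 2 x 168 x 0.051 = 17.14 mSv. At 112 MBq the corresponding values are 7.62 and 11.42 mSv.

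**The case against.** The strongest reply is that nothing in 8.1 is miscalculated. Twice 4.76 is 9.52, the percentage follows, and the voiding condition is printed in 4.1 of the same document. The procedure also leans towards voiding: participants drink water beforehand, void within about an hour of injection, and leave soon after a short scan. A list of scan-day steps would not normally record voids after dismissal, and consent pages are not available here, so an instruction to void may exist out of view. All of this stands. It means 4.76 mSv is plausible. It does not make an unconditional 4.76 mSv consistent with 4.1, because the documents do not show that the one required void earns the full reduction.

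A second reply is that RM2 has a nominal activity with a tolerance and 8.1 labels its figure as being for 140 MBq, whereas PSMA-11 is prescribed as a range, so quoting its maximum is natural. This stands too, and makes the 168 MBq figures optional.

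A third is that the effect is modest on total study exposure. With PSMA-11 included, the total moves from 13.36 + 9.52 = 22.88 mSv to 13.36 + 14.28 = 27.64 mSv, about 21% more. That is fair context, but 8.1 reports the agents separately and the RM2 line is the one affected.

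A reader might also go too far the other way and take 17.14 mSv as an upper bound. The documents do not support that: 0.051 is a mean coefficient, its voiding assumption is not stated, and the 7.7 mSv in 4.1 would give 2 x 168 x 0.055 = 18.48 mSv.

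**Conclusion.** The point holds as an unqualified safety figure. At 140 MBq, 8.1 gives the favourable end (9.52 mSv) as the only value, while the mean coefficient in 4.1 gives 14.28 mSv, 1.5 times as much and above the 13.36 mSv quoted for PSMA-11. The dose under the visible procedures probably lies between the two, assuming the required void earns some but not all of the reduction. The 7.7 against 7.14 mismatch in 4.1 is a separate, smaller error.

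Three stronger inferences are not supported. The first is that 9.52 mSv is false or 14.28 mSv is the true dose: the documents do not locate the value. The second is that RM2 is in fact the higher-dose agent: by the calculation above, that needs less than about 19% of the voiding reduction to be earned. The third is that participants were misinformed: the consent text is not visible.

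The percentages rest on the assumed 50 mSv limit. The point is worth fixing because it concerns a stated risk figure and the change is small.

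**What to change.** In 8.1, state the two-scan RM2 dose at 140 MBq as 9.52 mSv with 1-h voiding and 14.28 mSv at the reported mean coefficient, about 19% to 29% of the annual worker limit (name the limit; 50 mSv is assumed here).

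In 4.1, correct 7.7 to 7.14 mSv, or correct the inputs. If 7.7 is right, the second figure in 8.1 becomes 15.40 mSv.

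Optionally, to match the maximum-activity convention used for PSMA-11, add that at 168 MBq the corresponding figures are 11.42 and 17.14 mSv, describing the latter as the value at the mean coefficient and not as an upper bound. If participant-facing text repeats 9.52 mSv, carry the change there.

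The cost is a sentence or two in 8.1, one number in 4.1, and a less favourable stated exposure. No endpoint, sample size, procedure or analysis changes.

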2.5 Study Design

This is a pilot study with a total of 20 participants with known prostate cancer, scheduled to undergo HIFU local therapy. All patients will first be seen by a Stanford Cancer Institute physician and then referred if appropriate on clinical grounds to Dr [name] or his colleagues for this study. Eligible participants will undergo baseline assessments at enrollment. The following steps will take place after the participant has signed the written consent (participants will be randomized to have ^{68}Ga -RM2 first followed by ^{68}Ga -PSMA11 within 2 weeks or ^{68}Ga -PSMA11 first followed by ^{68}Ga -RM2 within 2 weeks [50/50 chance for each schedule]). After the 1st scan, the 2nd scan will only occur after the follow-up with the patient for the 1st scan, and after a minimum of 3 days have elapsed.

Scan 1

1. Participants will be given a copy of the consent form s/he signed
2. Participant will be asked to drink 1 to 2 glasses of water before arrival at the clinic
3. Vital signs (heart rate, blood pressure) will be recorded
4. Participant will be injected IV with $140 \pm 20\%$ mBq of ^{68}Ga -RM2 **OR** 3 to 7 mCi of ^{68}Ga -PSMA11.
5. Participant will void immediately prior to the scan
6. Approximately 45 minutes after the radiopharmaceutical IV administration, data acquisition will begin in the pelvic region and move toward the head. First, localizer MRI scans will be performed to define the table positions. After correct positioning of the spatial acquisition windows is ensured, the combined PET/MRI acquisition will be initiated with 3 to 5 table positions at a 2 to 4-min acquisition time per table position.
7. Participants will be dismissed.
8. Vital signs (heart rate, blood pressure) will be recorded again at the completion of the study
9. Participants will be contacted at 24 to 72 hours following the scan in order to capture potential occurring Adverse Events.

Scan 2

1. Participant will be asked to drink 1 to 2 glasses of water before arrival at the clinic
2. Vital signs (heart rate, blood pressure) will be recorded
3. Participant will be injected IV with 3 to 7 mCi of ^{68}Ga -PSMA11 **OR** $140 \pm 20\%$ mBq of ^{68}Ga -RM2 (ie, the radiopharmaceutical not administered for Scan 1)

4. Participant will void immediately prior to the scan

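### Section 8.1 states the RM2 dose (4.76 mSv per scan, 9.52 mSv for two) without the hourly voiding that 4.1 attaches to it, and 9.52 mSv does not cover the permitted 168 MBq even with that voiding

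*Combined protocol and SAP*

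**What the plan says.** Section 8.1 (Potential Adverse Events) is the protocol's statement of research radiation risk. For RM2 it says "The amount of radiation from one administration of 140 mBq of ^{68}Ga -RM2 is 4.76 mSv". It then gives 9.52 mSv for the pre- and post-treatment scans together, and describes this as about 20% of a radiation worker's yearly limit. Voiding is not mentioned.

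Section 4.1 is the source of the figure. It reports "The mean effective dose (14) was 0.051 mSv/MBq". From this coefficient the section concludes that "the effective dose from a 140 MBq injected radioactivity is 7.7 mSv". The lower value appears there only as a conditional possibility, in these words: "which could be reduced to roughly 4.76 mSv with frequent bladder voiding (1-h voids". On organ doses, the same section says "The organ with the highest absorbed dose was the urinary bladder wall at 0.61 mSv/MBq". The administered activity is 140 MBq plus or minus 20%, that is 112 to 168 MBq (the documents print mBq in places; MBq is meant).

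On voiding, the steps for each scan in 2.5 contain one instruction: "Participant will void immediately prior to the scan". Acquisition starts about 45 minutes after injection for Scan 1 and 45 to 60 minutes for Scan 2. Participants are also asked to drink one or two glasses of water before arriving. No later void is listed in 2.5, and sections 5.2, 6.2 and 7 add none.

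PSMA-11 is handled differently. Section 4.1 states "We used the maximum potential administered activity of 7 mCi and the higher of the reported dosimetry values", and 8.1 carries the resulting 6.68 mSv (13.36 mSv for two scans) forward.

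**The concern.** A dose that 4.1 makes conditional appears in 8.1 as a plain fact. The condition is a behaviour, repeated hourly voiding, and the listed procedures secure only one void. The risk statement therefore rests on the most favourable basis in the document.

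Three things are at stake. First, 8.1 may understate exposure. Second, the bladder wall receives the highest RM2 dose, so voiding is the obvious protective measure, and leaving it out of the steps may forgo a real reduction. Third, 8.1 sets a worst-case PSMA-11 figure beside a best-case RM2 figure at nominal activity, so the two tracers cannot be compared as printed. Each participant is scheduled for "2 separate clinic visits not less than 3 days apart for imaging before therapy and two separate clinic visits for imaging after therapy", so both figures apply to the same person.

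**Working it through.** **Inputs.** From 4.1: RM2 coefficient 0.051 mSv/MBq (printed twice); 7.7 mSv for 140 MBq; about 4.76 mSv with 1-h voids; RM2 activity 112 to 168 MBq; PSMA-11 259 MBq at 0.0258 mSv/MBq. From 8.1: 4.76 and 9.52 mSv for RM2; 6.68 and 13.36 mSv for PSMA-11; about 20% and 26% of the worker limit.

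**Formula.** Effective dose = activity x coefficient x number of scans, taking dose as proportional to activity.

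**Reproducing the plan's figures.**
- RM2 in 8.1: 2 x 4.76 = 9.52 mSv. The multiplication is right.
- PSMA-11: 259 x 0.0258 = 6.68 mSv; 2 x 6.68 = 13.36 mSv. Both agree.
- Coefficient behind 4.76: 4.76 / 140 = 0.034 mSv/MBq, which is the 1-h-void basis.
- RM2 in 4.1: 0.051 x 140 = 7.14 mSv, not 7.7. Conversely, 7.7 / 140 = 0.055 mSv/MBq, or 7.7 / 0.051 = about 151 MBq. The two entries in 4.1 do not agree.

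**Two RM2 scans under each basis (mSv).**

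| Activity | 0.034 (1-h voids) | 0.051 (printed coefficient) | 0.055 (implied by 7.7) |
|---|---|---|---|
| 112 MBq | 7.62 | 11.42 | not needed |
| 140 MBq | 9.52 | 14.28 | 15.4 |
| 168 MBq | 11.42 | 17.14 | 18.48 |

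Per scan at 168 MBq: 168 x 0.034 = 5.71 mSv; 168 x 0.051 = 8.57 mSv.

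**Size of the gap.**
- At 140 MBq the stated total lies between 0% and 33% below the dose on the 0.034 to 0.051 range (1 - 9.52/14.28 = 33.3%).
- At 168 MBq even the 1-h-void dose is 20% above the stated total (11.42/9.52 = 1.20).
- At 112 MBq the range 7.62 to 11.42 contains 9.52, so no understatement is shown.

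**Share of the worker limit.** The limit is not stated. The printed percentages imply 13.36/0.26 = 51.4 mSv and 9.52/0.20 = 47.6 mSv. Over that range 14.28 mSv is about 28% to 30%, and 15.4 mSv about 30% to 32%, against the printed 20%.

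**The case against.** The strongest reply is that voiding is not absent. Each scan includes a void within about an hour of injection, after fluid intake, and that void removes some activity. The documents give no dose for one void, nor do they say what voiding pattern underlies 0.051 mSv/MBq. A reader might infer that two scans really deliver 14.28 mSv; the documents do not support that. It is the unreduced figure, and the dose under the listed steps may be lower. A reader might also infer that 9.52 mSv is too low across the whole permitted activity range; the 112 MBq row shows otherwise.

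It can also be said that the consent pages and some other pages were not available for this review, and an instruction to keep voiding after the scan would naturally sit there. This stands: it cannot be concluded that participants receive no such instruction. It does not repair 8.1, which would still omit the condition.

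Thirdly, 8.1 names its basis openly (140 MBq for RM2, the maximum for PSMA-11) and its multiplication is correct. That is fair. The fault in 8.1 is a missing condition and an uncovered activity range; the only numerical inconsistency is in 4.1.

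**Conclusion.** The point holds as a gap between 4.1 and 8.1. The stated 9.52 mSv is right only for 140 MBq with 1-h voiding, and the visible procedures do not secure that voiding. At 140 MBq the two-scan dose lies between 9.52 and 14.28 mSv on 4.1's coefficients, or up to 15.4 mSv if the printed 7.7 is correct. At 168 MBq it is 11.42 to 17.14 mSv, so the stated figure falls short there whatever the voiding.

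This assumes that dose scales with activity and that one void gives a dose somewhere between the 1-h-void and unreduced values. It would be tempting to call 17.14 mSv the maximum. That is not safe until 7.7 and 0.051 are reconciled, because 0.055 mSv/MBq would give 18.48 mSv.

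The matter concerns participant safety information and is worth correcting. It does not touch the endpoint, the sample size or the success rule.

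**What to change.** Choose one of two routes.

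(a) In 2.5, for each RM2 scan, add an instruction to void after the scan and hourly for a stated period. In 8.1, say that 4.76 mSv at 140 MBq (5.71 mSv at 168 MBq) assumes this. This route is preferable because it may lower the dose as well as correct the text.

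(b) Leave the procedures alone and give the unreduced dose in 8.1. If 0.051 mSv/MBq is confirmed, that is 7.14 mSv per scan at 140 MBq and 8.57 mSv at 168 MBq, or 14.28 and 17.14 mSv for two. Update the percentage of the worker limit to match.

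Under either route, check 7.7 mSv in 4.1 against the dosimetry source, correct whichever of 7.7 and 0.051 is wrong, and call no figure a maximum before then. A four-scan total per participant (13.36 + 9.52 = 22.88 mSv on the present text) and the name of the annual limit would help the reader but are optional.

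The cost is one procedure line and some rewording: a small voiding burden under (a), or a less favourable stated exposure under (b). Administered activities do not change.
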